This pilot study is being conducted to assess the feasibility of recruiting patients and clinician adherence to steroid protocol, to refine the trial intervention and endpoints, and to calculate target sample sizes in preparation for a larger pragmatic clinical trial comparing the two approaches to corticosteroid administration.

Specific Aim 2: To evaluate the trajectories of C-reactive protein (CRP), pulmonary and non-pulmonary organ failures over time in patients from the two study arms.

In addition to assessing the feasibility of individualized, biomarker guided steroid dosing, this pilot study is necessary to evaluate the usefulness of CRP as a predictive enrichment tool in identifying patients in whom steroid administration will be most beneficial and also as a prognostic enrichment tool (alongside severity of pulmonary and other organ failures) to identify patients at higher risk of poor outcomes. It will inform the target population and will help refine the thresholds for initiation, titration and discontinuation of individualized corticosteroid therapy used to reduce inflammation in patients with pneumonia and acute hypoxic respiratory failure

Specific Aim 3: To evaluate the role of a biomarker-titrated adjuvant corticosteroid administration compared to usual care in patients admitted to hospital with SARS Co-V 2 (COVID-19) infection. We hypothesize that, compared to usual care, individualized biomarker-titrated dosing will be associated with:

- a) Improvement in pulmonary organ function based on requirements for oxygen and advanced respiratory support

- b) Reduced hospital length of stay
- c) Reduced cardiovascular complications including evidence of myocardial injury, need for inotropes and new/worsening arrhythmias

II. Background and Significance

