Hyperglycemia	30 (23.8%)	26 (23.4%)	0.94

[figure not shown]
Team experience: [name] is an Assistant Professor and Senior Associate Consultant in the Division of Pulmonary and Critical Care at the Mayo Clinic. He has expertise in ARDS epidemiology research and the incorporation of biomarkers in ARDS risk prediction. [name] is a clinical fellow in Critical Care at Mayo Clinic, Rochester with an interest in critical care outcomes research. [name] is a research trainee at Mayo Clinic, Rochester also with an interest in critical care outcomes research. [name] is an assistant professor and clinical pharmacist at Mayo Clinic, Rochester with an interest in individualizing pharmacotherapy for critically ill patients with infections. [name] is an internationally renowned leader in ARDS research and founder of our multidisciplinary clinical research laboratory (METRIC), and Director of Critical Care Research at Mayo. Within this group, we have adequate resources, expertise and training to achieve our scientific objectives.

IV. Research Design and Methods

Figure 1 summarizes study design. A two-arm multicenter randomized trial

Hospital presentation:
Emergency Department

Adult Patient with Pneumonia + Acute Hypoxic Respiratory Failure

A. Study Design or Overview

Specific Aims 1 and 3: We plan to perform a two arm multi-center pilot phase II clinical trial. 44 patients with pneumonia (additional strata to include patients with COVID-19 for specific aim 3) and acute respiratory failure defined by $\text{SpO}_2/\text{FiO}_2 < 315$ ($\text{SpO}_2 < 90\%$ on room air or $< 97\%$ on 2L/min O_2) will be included.

- Control arm: Usual care
- Intervention arm: individualized, biomarker concordant steroid use: dosing, titration and duration according to CRP level (Table 3).

Table 3. Biomarker-concordant steroid treatment

CRP (mmol/L)	Methylprednisolone (daily)
<50	None
51 - 100	0.5 mg/kg
101 - 150	0.75 mg/kg
151 - 200	1 mg/kg
>200	1.5 mg/kg

*per ideal body weight

Randomization will be stratified based on the need for high flow nasal cannula oxygen, noninvasive or invasive ventilator support.

Definitions

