- No data will be disclosed to another institution and all identifiers linking to the patient will be destroyed after data collection is complete.

f. Data Analysis

Aims 1 and 3: Continuous outcomes will be compared between treatment arms using linear regression and binary outcomes using chi-square or fishers exact tests. Secondary outcomes will be tested without adjustment for multiple comparisons. Data from this study, including estimated effects of the intervention and sample variation in outcomes, will provide valuable information to plan a well-powered subsequent phase II trial.

Aim 2: The correlation between CRP levels and corticosteroid dosing in those who receive individual-dose steroids versus usual care will be examined using Pearson's correlation coefficient. The effect of CRP levels on the secondary outcomes will be evaluated using multivariable analysis adjusting for severity of illness. The data from this study will help evaluate the usefulness of CRP as a predictive and prognostic enrichment tool and thus help inform and refine the thresholds for initiation, titration and discontinuation of corticosteroids in the subsequent larger study.

Decision to proceed with a larger study: The decision to proceed with a phase II/III study will be based on the following criteria:

- Ability to enroll an adequate number of eligible patients early in the course of illness. The expected hurdles include delayed identification of potentially eligible patients, provider/patient refusal, non-adherence to protocol, and inability to obtain CRP levels in a timely manner.
- Safety; i.e. absence of significant adverse events.

- Preliminary efficacy: ability to show reduction in steroid use, reduced episodes of hyperglycemia and favorable trajectory of pulmonary organ dysfunction.

The data collected will be essential to adequately plan the future study, estimate power and sample size, refine exclusion/inclusion criteria and determine the number and characteristics of future study sites.

g. Feasibility and Time Frame:

We believe that our project is feasible in the time frame of the grant; we hope to use the preliminary data generated from this pilot study to decide about moving forward with a phase II/III study involving a larger study group and more centers (Table 5).

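### Aim 2 sets out to evaluate CRP trajectories by arm and CRP as a predictive tool, but no analysis of daily CRP by arm is stated and no CRP-by-arm term is named

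*Combined protocol and SAP*

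**What the plan says.** Specific Aim 2 (section I) has two parts that matter here. The first is to "evaluate the trajectories of C-reactive protein (CRP), pulmonary and non-pulmonary organ failures over time in patients from the two study arms". The second is to "evaluate the usefulness of CRP as a predictive enrichment tool in identifying patients in whom steroid administration will be most beneficial", alongside a separate prognostic use.

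The Aim 2 paragraph under Data Analysis (section IV.f) states two analyses:

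- "The correlation between CRP levels and corticosteroid dosing in those who receive individual-dose steroids versus usual care will be examined", by Pearson's coefficient.
- "The effect of CRP levels on the secondary outcomes will be evaluated using multivariable analysis adjusting for severity of illness".

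It then says that the data will "help evaluate the usefulness of CRP as a predictive and prognostic enrichment tool", and so help refine the steroid thresholds for the larger study.

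The only between-arm method in the plan belongs to Aims 1 and 3: "Continuous outcomes will be compared between treatment arms using linear regression", with chi-square or Fisher's exact tests for binary outcomes. CRP is not in the list of primary and secondary outcomes. SOFA at ICU admission and after 24, 48 and 72 hours is.

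CRP is to be measured daily in both arms for the first 5 days or until discharge (section IV.B, Protocol). The usual-care results are withheld from the treating physicians. In the intervention arm, Table 3 sets the daily dose from the CRP band.

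**The concern.** A prognostic marker says who does badly. A predictive marker says for whom the treatment effect is larger. The second question needs the treatment contrast to be allowed to vary with the marker, and neither stated Aim 2 analysis is described as doing that. The Pearson coefficient relates CRP to dose and involves no outcome. The severity-adjusted model is described by one effect of CRP.

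The trajectory part of the aim has a similar gap. Five days of CRP are collected in both arms, yet no method is stated for summarising or comparing them by arm.

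At stake is what the next trial takes from this pilot. If a prognostic slope is carried forward as evidence of who benefits from steroids, the target population and thresholds would rest on an analysis that did not address that question.

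**Working it through.** The documents give no figure for Aim 2, so there is nothing to reproduce. The check has a text part and three calculations.

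**1. Aim against analysis**

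| Aim 2 element | Stated analysis |
|---|---|
| CRP over time, by arm | None |
| Organ failure over time, by arm | Partly covered: SOFA at four times is a secondary outcome under the Aims 1 and 3 regression |
| CRP as prognostic tool | Severity-adjusted CRP effect |
| CRP as predictive tool | None named |

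**2. What a single CRP coefficient shows**

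Let the CRP slopes be b0 (usual care) and b1 (intervention). With equal allocation (assumed; the documents give no ratio) and the same CRP distribution in both arms, a model without an interaction estimates (b0 + b1)/2. The interaction is b1 - b0.

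| b0, b1 | Single coefficient | Interaction |
|---|---|---|
| -1, -1 | (-1 - 1)/2 = -1 | 0 |
| 0, -2 | (0 - 2)/2 = -1 | -2 |
| -2, 0 | (-2 + 0)/2 = -1 | +2 |

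A simulation of 200,000 patients, with CRP and severity correlated at 0.4 (assumed), gave single coefficients of -1.00, -0.99 and -1.00, the same with or without an arm main effect. The fitted interactions were 0.00, -2.00 and +2.00. The single coefficient cannot tell the three cases apart.

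**3. Precision of an added CRP-by-arm term**

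Inputs: 44 patients (section IV.A), 22 per arm (assumed), residual SD 1, CRP in SD units. The model has six parameters: intercept, arm, CRP, CRP x arm, severity and one binary stratum. That leaves 44 - 6 = 38 degrees of freedom.

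- Without covariates, the SE is roughly sqrt(1/22 + 1/22) = 0.30.
- Over 4,000 simulated trials with the covariates, the median SE was 0.323.
- 95% half-width = 2.024 x 0.323 = 0.65 outcome SD per SD of CRP.

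**4. How much interaction Table 3 creates by itself**

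Suppose CRP has no predictive role: every mg/kg gives the same benefit k, and usual-care dose is unrelated to CRP. Then

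CRP x arm = -k x (slope of Table 3 dose on CRP, in mg/kg per SD of CRP).

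The CRP distribution is assumed lognormal with medians 80, 120, 150 and 200 and log-SDs 0.5, 0.7 and 0.9 (12 combinations). One CRP value stands for exposure. A value of exactly 50, which falls in no band of Table 3, was put in the lowest band for this calculation only.

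Across raw and log CRP the dose slope runs from about 0.26 to 0.50 mg/kg per SD. At k = 1 outcome SD per mg/kg, the interaction is therefore about -0.26 to -0.50. At k = 0.5 it is half that, about -0.13 to -0.25.

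If usual-care dose also rises with CRP, the formula becomes -k x (Table 3 slope - usual-care slope). The term then shrinks, and it changes sign if the usual-care slope is the larger. The usual-care slope depends on the spread of usual-care doses, which the documents do not give.

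**The case against.** - **The term is not excluded.** *Multivariable* could cover a CRP-by-arm interaction. This stands. A reader might infer that the plan specifies a wrong model, and the text does not support that. It leaves the one term the predictive question needs unnamed, and so open to choice after the data are seen.
- **Aim 2 promises to evaluate, not to compare or test.** This also stands. A descriptive display of daily CRP by arm would meet the wording, and a mixed model is one good choice among several. What is missing is any stated method.
- **The interaction would not establish prediction anyway.** This is the strongest objection, and it is correct. Calculation 4 shows that the term mixes effect modification with dose. It concerns the dosing strategy, not steroid against no steroid. The conclusion is therefore to narrow the claim, with the added term as a supporting exploratory estimate.
- **It is a 44-patient pilot.** Section IV.C disclaims power for efficacy on patient-centred outcomes. The same section says that the pilot is to supply effect sizes, so an estimate with an interval fits its purpose; a test does not.

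A reader might also infer that the CRP-dose correlation is meant as evidence of benefit or as the adherence measure. The documents say neither. It is only to be examined, and adherence is already the primary feasibility outcome.

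**Conclusion.** The gap is real and follows from the text alone: Aim 2's trajectory and predictive elements have no stated analysis for CRP, and the one outcome model described speaks to prognosis. The numerical illustrations rest on assumptions: equal allocation, 22 per arm, the assumed CRP distributions, and a constant benefit per mg/kg. The dose-driven figure of -0.26 to -0.50 holds only if usual-care dose is unrelated to CRP.

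It would be tempting to say that the decision to run the larger trial is compromised. The documents do not support that. The three criteria for proceeding are enrolment, safety and preliminary efficacy. CRP enters them only as a practical hurdle (obtaining results in time), not through any CRP-outcome result. The primary feasibility outcome and participant safety are likewise unaffected. What is affected is the use of Aim 2 to refine thresholds and target population. A low-priority *should* is the right weight.

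**What to change.** 1. **Trajectories.** State an analysis of daily log-CRP by arm using all available days. One suitable choice is a mixed model with arm x day, adjusted for the randomisation stratum ("Randomization will be stratified based on the need for high flow nasal cannula oxygen, noninvasive or invasive ventilator support"). Report discharges and deaths by arm within the 5-day window, since the CRP series stops at discharge.
2. **CRP-by-arm estimate.** For continuous secondary outcomes, add first available CRP x arm to the severity-adjusted model. Flag values taken after randomisation or after a steroid dose: the plan admits patients already given a first dose and guarantees no pre-randomisation CRP. Report the estimate with its confidence interval as exploratory, not as a test.
3. **Wording.** Narrow *predictive* in Data Analysis. Say that the interaction concerns the dosing strategy and that, because Table 3 makes the arm difference in steroid exposure vary with CRP, it can arise with no predictive role for CRP.

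The cost is SAP wording and a little analysis work on data already planned, with no change to dosing or procedures. The downside is that the estimates will be imprecise, and the interaction cannot be separated from dose. A mixed model also assumes that dropout at discharge depends only on observed values.
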